### 1.2 Study objectives, endpoints and estimands

Table 1-1 Objectives and related endpoints

Objective(s)	Endpoint(s)		
Primary objective(s)	Endpoint(s) for primary objective(s)		
Evaluate the region-level correct localization rate (CLR) of [18F]CTT1057	Proportion of regions containing at least one TP lesion (anatomically localized correspondence between PET imaging and the reference standard), regardless of any coexistent FP findings within the same region, out of all regions containing at least one PET-positive finding by central assessments. See Section 1.2.1 for Primary Estimand		
Evaluate the patient-level positive predictive value (with anatomical localization) of [18F]CTT1057	
 
Proportion of patients who have at least one TP lesion (anatomically localized correspondence between PET imaging and the reference standard), regardless of any co- existent FP findings, out of all patients who are PET/CT scan positive by central assessments.
 
See Section 1.2.1 for Primary Estimand
 
		
Secondary objective(s)	Endpoint(s) for secondary objective(s)		

 
Evaluate the patient-level sensitivity of [18F]CTT1057
 
	
 
Proportion of patients that test positive on [¹8F]CTT1057 and CTS (TP) among those that are CTS positive (TP or FN)
 
		

	ojective(s)	Endpoint(s)			
 		EII			
•	Evaluate the patient-level specificity of [  F]CTT1057	•	Proportion of patients that test negative on [18F]CTT1057 and CTS (TN) among those that are CTS negative (TN or FP)		
•	Evaluate the patient-level negative predictive value of [  F]CTT1057	•	Proportion of patients who are both [18F]CTT1057 and CTS negative (TN) among those who test negative on [18F]CTT1057 (TN or FN)		
•	Evaluate the patient-level accuracy of [18F]CTT1057	•	Proportion of patients that are CTS and [18F]CTT1057 positive (TP) and negative (TN) among those patients that identified on [18F]CTT1057 (TP, TN, FP or FN)		
•	Evaluate correct detection rate (CDR)	•	Proportion of patients who have at least one TP lesion (exactly localized correspondence between PET imaging and the reference standard), regardless of any co-existent FP findings, out of all patients who are scanned		
•	Evaluate detection rate	•	Proportion of patients who have at least one PET positive lesion, regardless of TP or FP findings, out of all patients who are scanned		

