•	Evaluate the region level sensitivity of [  F]CTT1057	•	Proportion of regions that test positive on both [18F]CTT1057 and CTS (TP) among those regions that are CTS positive (TP or FN)		
•	Evaluate the region level specificity of [  F]CTT1057	•	Proportion of regions that test negative on both [18F]CTT1057 and CTS (TN) among those regions that are CTS negative (FP, or TN)		
•	Evaluate the region level negative predictive value of [  F]CTT1057	•	Proportion of regions that are CTS and [18F]CTT1057 negative (TN) among those regions that test negative on [18F]CTT1057 (TN or FN)		
•	Evaluate the region level accuracy of [  F]CTT1057	•	Proportion of regions that are CTS and [18F]CTT1057 positive (TP) and negative (TN) among those regions that identified on [18F]CTT1057 (TP, TN, FP and FN)		
•	Evaluate the patient-level positive predictive value related to PSA levels	•	Percentage of patients who have at least one TP lesion (exactly anatomically localized correspondence between [18F]CTT1057 PET imaging and the reference standard), regardless of any co-existent FP findings, out of all patients who are [18F]CTT1057 positive, stratified by PSA levels		
•	Characterize the safety and tolerability of [18F]CTT1057	•	Incidence of AEs. Treatment emergent adverse event (TEAE) rate within 14 days after each PET tracer administration		
•	[  F]CTT1057 scan inter-reader variability	•	Inter-reader agreement of [18F]CTT1057 images		
•	[  F]CTT1057 scan intra-reader variability	•	Intra-reader agreement of [18F]CTT1057 images		

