#### 2.6.1 Secondary endpoint(s)

For the following secondary endpoints, centralized imaging assessments (CTS Level 2) will be used as reference standard if pathology assessment (CTS Level 1) is not available for a lesion, inconclusive or negative (for biopsy only).

**Patient-level sensitivity** is defined as the proportion of TP participants among those who are TP or FN

**Patient-level specificity** is defined as the proportion of TN participants among those who are TN or FP

**Patient-level negative predictive value** is defined as the proportion of TN participants among those who are TN or FN

Patient-level accuracy is defined as the proportion of TP and TN participants among all scanned participants (regardless of TP, TN, FP, FN)

**Patient-level correct detection rate** is defined as the proportion of TP participants among all scanned participants (regardless of TP, TN, FP, FN)

**Patient-level detection rate** is defined as the proportion of TP and FP participants among all scanned participants (regardless of TP, TN, FP, FN)

where TP, TN, FP, FN participants are defined as follows:

- PSMA TP participants are those who have at least one TP lesion (with anatomically localized correspondence between [18F]CTT1057 PET imaging and the CTS).
- PSMA TN participants are those who do not show any pathological [F]CTT1057 uptake and will be confirmed as NOT having any lesions with the CTS.
- PSMA FP participants are those who show at least one pathological [18F]CTT1057 uptake but will be verified as NOT having any lesions with the CTS or no lesions are correctly localized in anatomical location by the CTS.
- PSMA FN participants are those who do not show any pathological [18F]CTT1057 uptake but will be confirmed as having at least one lesion with the CTS.

Number of TP, TN, FP, FN participants will be presented and used to calculate the diagnostic performance parameters.

Two-sided exact binomial 95% CIs will be calculated for patient-level diagnostic performance parameters.

[F]CTT1057 scan inter-reader variability is defined as agreement among three readers determinations and will be assessed by Fleiss' Kappa statistic.

[18F]CTT1057 scan intra-reader variability is defined as within-reader agreement for two different time points and will be assessed by Cohen's Kappa statistic. A subset of imaging reading will be performed at two different time points by each reader. See details in imaging charter.

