Change in patient management plans attributed to the [18F]CTT1057 PET/CT scan is defined as the percentage of participants who undergo a change in intended treatment plan attributed to

the PET/CT scan as assessed by pre-imaging questionnaire 1 and post-imaging questionnaire 2.

The number and percentage of participants from the F-SAF for each of the following categories of treatment plan in each of the two questionnaires will be calculated: surgery, radiation alone, radiation alone with change in radiation treatment plan (only applicable for questionnaire 2), radiation plus ADT, ADT alone, observation/surveillance, other (free text box).

Treatment plan change is defined as a change in the pair of categories (one category of questionnaire 1, one category of questionnaire 2).

The number and percentage of participants from the F-SAF with treatment plan change as defined above will be calculated. Shift tables comparing treatment plans between questionnaire 1 and 2 will be displayed. The number (%) of participants with and without a change in treatment plans by [18F]CTT1057 local read results (i.e. positive, negative, and inconclusive) will be tabulated.

**Region-level sensitivity** is defined as the proportion of TP regions among those that are TP or FN

**Region-level specificity** is defined as the proportion of TN regions among those that are TN or FP

**Region-level negative predictive value** is defined as the proportion of TN regions among those that are TN or FN

**Region-level accuracy** is defined as the proportion of TP and TN regions among those that are identified on [18F]CTT1057 (regardless of TP, TN, FP, FN)

where TP, TN, FP, FN regions are defined as follows:

- PSMA TP regions are regions containing at least one TP lesion (anatomically localized correspondence between [18F]CTT1057 PET imaging and the CTS).
- PSMA TN regions are regions containing no lesions with pathological [18F]CTT1057 uptake and confirmed by CTS.
- PSMA FP regions are regions containing lesions with pathological [F]CTT1057 uptake but are verified negative by CTS or none is correctly localized in anatomical location by the CTS.
- PSMA FN regions are regions containing no lesions with pathological [F]CTT1057 uptake but are confirmed as having at least one lesion with the CTS.

Number of TP, TN, FP, FN regions will be presented and used to calculate the diagnostic performance parameters.

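### CTS-positive cases whose only PET uptake is unmatched are counted as FP and never FN, so sensitivity and specificity do not use the denominators set in Table 1-1

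*SAP*

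**What the plan says.** SAP Table 1-1 defines the denominators by disease status under the composite truth standard. Patient-level sensitivity is taken "among those that are CTS positive (TP or FN") and patient-level specificity "among those that are CTS negative (TN or FP"). The region-level rows follow the same pattern, with specificity "among those regions that are CTS negative (FP, or TN"). Protocol Table 2-1 agrees.

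SAP 2.6.1 then gives the formulas TP/(TP+FN) and TN/(TN+FP) and defines the four labels:

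- **FP participant:** PET uptake is present, and either the CTS shows no lesion "or no lesions are correctly localized in anatomical location by the CTS".
- **FN participant:** "PSMA FN participants are those who do not show any pathological" uptake but have at least one CTS lesion.
- **FP region:** there is uptake in the region, "but are verified negative by CTS or none is correctly localized in anatomical location by the CTS".
- **FN region:** there is no uptake in the region, but the CTS confirms a lesion there.

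One set of counts serves every measure: "Number of TP, TN, FP, FN participants will be presented and used to calculate the diagnostic performance parameters". Protocol 12.5.1 has the same definitions. SAP Section 4, which lists departures from the protocol analyses, does not mention the difference.

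**The concern.** The second limb of the FP definition is an alternative to the CTS showing no lesion, so it covers participants who do have CTS-confirmed disease. By Table 1-1 such a participant is CTS-positive and belongs in the sensitivity denominator. By 2.6.1 he is FP, which puts him in the specificity denominator and out of the sensitivity calculation. A scan that misses all confirmed disease and marks something else then costs nothing in sensitivity, while a diseased participant is treated as disease-free for specificity.

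Table 1-1 is also loose about the sensitivity numerator. It asks for a positive result on both PET and CTS and does not mention location. The correct detection rate row of the same table does ask for "exactly localized correspondence between PET imaging and the reference standard", and so, in substance, does the TP definition in 2.6.1. The direction of the sensitivity error depends on which reading is meant.

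Two analysts, one working from Table 1-1 and one from 2.6.1, could report different sensitivity and specificity from the same data.

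**Working it through.** **Which cells conflict.** Cross-classify by PET result, CTS result and anatomical match:

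| PET | CTS | Match | SAP 2.6.1 label | Denominator used by 2.6.1 | Denominator by Table 1-1 |
|---|---|---|---|---|---|
| + | + | yes | TP | sensitivity | sensitivity |
| + | + | no | FP | specificity | sensitivity |
| + | − | – | FP | specificity | specificity |
| − | + | – | FN | sensitivity | sensitivity |
| − | − | – | TN | specificity | specificity |

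Only the second row conflicts. At region level it arises only when the unmatched uptake and the CTS lesion lie in the same region; a diseased region with no uptake of its own is already FN.

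**Inputs for an illustration.** The documents state no sensitivity or specificity figure, so there is none to reproduce. From SAP 3 and 3.1:

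- 152 evaluable participants and an 80% PET-positive rate: 152 × 0.80 = 121.6, taken as 122.
- PPV of 0.33 under the alternative: 122 × 0.33 ≈ 40 TP, and 122 − 40 = 82 FP.
- PET-negative: 152 − 122 = 30 = FN + TN.

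Assumed, because the documents do not give them: the FN/TN split, and k, the number of the 82 FP cases that are CTS-positive.

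**Formulas.**

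- Specificity: as written TN/(TN + 82); CTS-negative only TN/(TN + 82 − k).
- Sensitivity: as written 40/(40 + FN); CTS-positive denominator with localised TP 40/(40 + FN + k); Table 1-1's bare numerator (40 + k)/(40 + FN + k).

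**Results with FN/TN = 10/20.** As written, specificity is 20/102 = 19.6% and sensitivity is 40/50 = 80.0%, whatever k is.

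| k | Specificity, CTS-negative only | Sensitivity, localised TP | Sensitivity, bare numerator |
|---|---|---|---|
| 0 | 20/102 = 19.6% | 40/50 = 80.0% | 40/50 = 80.0% |
| 2 | 20/100 = 20.0% | 40/52 = 76.9% | 42/52 = 80.8% |
| 6 | 20/96 = 20.8% | 40/56 = 71.4% | 46/56 = 82.1% |
| 12 | 20/90 = 22.2% | 40/62 = 64.5% | 52/62 = 83.9% |
| 24 | 20/78 = 25.6% | 40/74 = 54.1% | 64/74 = 86.5% |

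**Other splits, k = 12, localised TP.**

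- FN/TN = 5/25: specificity 25/107 = 23.4% against 25/95 = 26.3%; sensitivity 40/45 = 88.9% against 40/57 = 70.2%.
- FN/TN = 15/15: specificity 15/97 = 15.5% against 15/85 = 17.6%; sensitivity 40/55 = 72.7% against 40/67 = 59.7%.

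**A higher assumed PPV.** The 0.33 is a powering value. With PPV 0.80 (98 TP, 24 FP), FN/TN = 15/15 and k = 6, sensitivity is 98/113 = 86.7% against 98/119 = 82.4%, and specificity is 15/39 = 38.5% against 15/33 = 45.5%.

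**Measures that do not move.** The disputed case is PET-positive and is not a correctly localised result, so PPV, CLR, correct detection rate, detection rate and NPV are unchanged. Accuracy in the 10/20 example is (40 + 20)/152 = 39.5% for every k.

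No region-level figure is given, because the documents do not state the number of positive regions per participant.

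**The case against.** The strongest reply is that 2.6.1 is an explicit rule, repeated in both documents, and a programmer can execute it. One mutually exclusive four-cell table that gives credit only for localised findings is a coherent design, and the loose wording is in the objectives table. On this view a clause in Table 1-1, with disclosure, would be enough. It is true that the rule can be run. But running it gives a sensitivity that omits some diseased participants and a specificity that includes them. Editing Table 1-1 to match would make the documents agree without making either quantity what its name implies.

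A second objection is that matching detail may sit in the imaging charter or in redacted appendix pages. Those cannot be checked, but nothing visible refers to them for redefining these cells. If matching were by region alone, the region-level conflict would be empty. The FP-region wording suggests otherwise, since it allows uptake in a CTS-positive region that is still not correctly localised. The patient-level conflict does not depend on this.

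The remaining objections concern size, and they largely stand. The value of k is unknown. It may be small, because CTS Level 2 must include another PSMA-targeted PET, though the documents give no rate. At k = 2 the shifts are about 3 points in sensitivity and 0.4 in specificity. Even at k = 12, the 22.2% specificity lies inside the exact 95% interval for 20/102 (12.4% to 28.6%). Both measures are secondary with no success threshold, and SAP 1.2.1 acknowledges that true and false negatives are hard to establish in this setting.

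**Conclusion.** The concern holds. The cell definitions in SAP 2.6.1 and Protocol 12.5.1 contradict the denominators in SAP Table 1-1 and Protocol Table 2-1 for one cell: CTS-positive cases with only unmatched uptake. If there are any such cases, specificity is understated against Table 1-1. Sensitivity is overstated when TP requires localisation, as 2.6.1 has it; on Table 1-1's bare numerator it would instead be slightly understated.

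The sizes rest on an assumed k and FN/TN split and on the planning PPV of 0.33. They show that sensitivity can move by several points to more than 20, and specificity by less. The error is nil when k is zero. It is confined to secondary estimates and does not touch co-primary success. It should be corrected because the reported values otherwise depend on which part of the plan is followed.

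**What to change.** In SAP 2.6.1 and Protocol 12.5.1, make the cells specific to the measure, at patient and region level:

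1. For sensitivity only, count as FN every CTS-positive case with no anatomically matched PET lesion, whether or not unmatched uptake is present.
2. For specificity only, restrict FP to CTS-negative cases.
3. Keep the present FP rule for PPV, CLR, accuracy and detection rate, and keep the PET-negative FN for NPV. This has to be stated because 2.6.1 feeds one set of counts to all measures. If the wider FN reached NPV, the 10/20 example with k = 12 would fall from 20/30 = 66.7% to 20/42 = 47.6%.
4. State in Table 1-1 that TP requires localisation.
5. Report, per reader and at both levels, the number of CTS-positive cases with only unmatched uptake, so that readers can see whether the issue was material.

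The cost is a few sentences of definition and one derivation flag, with no new data. The protocol wording needs an amendment, or the change can be recorded in SAP Section 4. Reported sensitivity may fall.

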• 50% or greater decline in **PSA following radiation therapy** (as long as no concomitant androgen deprivation therapy (ADT) is given) as per PCWG3 criteria (Scher et al 2016).

In the cases where pathology will be available, assessments by the local pathologists will be performed as per SoC, and results should be available within 2 weeks after surgery. Pathologists will be blinded to any PSMA-PET data (i.e. both PET/CT scans). In this case, only pathology will be used as SoT for the concerned lesion(s).

In the cases where pathology will not be available for a lesion, the central read results of the [68Ga]Ga-PSMA-11 PET/CT scan (performed for all subjects randomized) and other imaging diagnostic procedures to be performed on each participant for the CTS level 2 will be used as SoT for the co-primary endpoint calculations. See Section 4.1 for central read details.

[figure not shown]
All patients will undergo a [⁶⁸Ga]Ga-PSMA-11 PET/CT as part of the study, for both the CTS Level 2 (in case it is required as SoT) and the secondary endpoint of assessment of concordance between [¹⁸F]CTT1057 and [⁶⁸Ga]Ga-PSMA-11 for detection of lesions (as detailed in Section 2).

In addition to central review, local review of SoC images (including [⁶⁸Ga]Ga-PSMA-11) will be performed to be used by the treating physician/Clinical Study Investigator for patient management decisions and overall assessment.

See Section 8.3.1 for assessment details and Section 6.4 for blinding requirements.

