A questionnaire on the planned patient management will be filled-in by the treating physician/Clinical Study Investigator before (questionnaire 1) and within 14 days after (questionnaire 2) knowing the results of the [18F]CTT1057 PET/CT scan. A local review of [18F]CTT1057 PET/CT images will also be performed by a local nuclear medicine physician or radiologist with expertise in reading oncology PET/CT scans and the results will be provided to the treating physician/Clinical Study Investigator for completion of questionnaire 2. Options will be given in the questionnaire to capture possible management plan, such as Surgery, Radiation alone, Radiation alone with change in radiation treatment plan (only applicable for questionnaire 2), Radiation plus ADT, ADT alone, Observation/surveillance, Other (free text box). Any change in patient management plan between the questionnaire 1 and questionnaire 2 should not be based only on [18F]CTT1057 PET/CT scan results since this is an investigational diagnostic imaging product. Other diagnostic procedures should be performed as per SoC in order to confirm and implement the changed management plan. See Figure 3-1 for study design schema.

Figure 3-1 Study Design

Screening period

Written informed consent form (ICF) must be obtained prior to any screening procedures. The participant must be registered in the Interactive Response Technology (IRT) for screening. All procedures described in the Assessment Schedule as per Table 8-1 must be carried out, prioritizing laboratory assessments to allow time to obtain the results at least 14 days prior the planned first PET imaging day (Day 1). Eligibility must then be confirmed at the latest on Day -14. The screening period should last up to 28 days.

Once eligibility is confirmed, the participants will be randomized in IRT to be assigned to one of the following two PET/CT scan sequences at random in a 1:1 ratio:

- Sequence 1: [¹⁸F]CTT1057 on Day 1 (investigational imaging agent of interest) followed by [⁶⁸Ga]Ga-PSMA-11 at least 14 days apart (as part of CTS if required, and for secondary endpoint)
- Sequence 2: [⁶⁸Ga]Ga-PSMA-11 (as part of CTS if required, and for secondary endpoint) on Day 1 followed by [¹⁸F]CTT1057 (investigational imaging agent of interest) at least 14 days apart

PET Imaging days

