The 2 PET imaging procedures will be done at least 14 days apart. The day of the first PET imaging agent injection will be considered study Day 1. Please refer to Section 8.3.1 for the steps that will take place on each PET imaging day.

Both visits will also be considered as the End of Treatment (EOT) visits.

Safety Checks

All treated participants will be contacted by phone within 24 to 72 hours following each PET/CT scan in order to capture potential occurring Adverse Events.

Safety Follow-up

Participants will come back to the hospital 14 days (+ 3 day window) after each PET/CT scan day, for a safety visit including vital signs, lab and urine analysis. For participants undergoing surgery, radiation therapy or initiating any antineoplastic medication (provided all CTS procedures have been completed before this initiation) prior to planned safety visit, these safety follow-up assessments will need to be performed before the surgery/radiation therapy/initiation of antineoplastic medication.

Additional Follow-up

Additional follow up period will be applicable where additional diagnostic procedures are to be performed. These may include SoC pathology, imaging or other modality disease assessments (CTS Levels 1 or 2) up to 8 weeks after [¹⁸F]CTT1057 PET/CT scan or three-month follow-up imaging (from baseline) where it is clinically required for the diagnosis of particular lesion(s).

In addition, in cases where the CTS Level 2 is not feasible/appropriate or inconclusive, and the CTS Level 3 will apply and will include the assessment of PSA levels prior to starting RT (which should commence within 8 weeks of completing [18F]CTT1057 PET/CT scan) and at approximately 90 days from last day of radiation.

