6.4 Treatment blinding

Novartis

Treatment and PET/CT scan sequence assignment will be open to participants, investigator staff, persons performing the assessments, and the study team. The following blinding is applicable in this study:

- [18F]CTT1057 PET/CT images will be submitted to a CRO for independent centralized read by 3 independent readers blinded to patient data collected in clinical database (such as medical history details or diagnostic test results).
- In addition, [18F]CTT1057 PET/CT images will be read by local nuclear medicine physician or radiologist with expertise in reading oncology PET/CT scans at each site, who will be blinded to [68Ga]Ga-PSMA-11 PET/CT imaging results, but not to other patient data. The results will be shared with the treating physician / Clinical Study Investigator to support the completion of the patient management questionnaire 2.
- Images from diagnostic procedures included in the CTS Level 2 will be submitted to a CRO for independent centralized read by independent readers, blinded to [18F]CTT1057 PET/CT images, but not to other patient data collected in clinical database.
- In addition, these CTS images will be read by a local nuclear medicine physician or radiologist with expertise in reading oncology PET/CT scans at each site as per SoC, who will be blinded to [18F]CTT1057 PET/CT imaging results, but not to other patient data.
- In the cases where pathology will be available, assessments by the local pathologists will be performed as per SoC. Pathologists will be blinded to any PSMA-PET data (i.e. both PET/CT scans).

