8.5.1 Other Assessments

Patient Management questionnaire will be completed by the treating physician/ Clinical Study Investigator before and within 14 days after having the results of the [¹⁸F]CTT1057 PET imaging assessment by an independent local nuclear medicine physician or radiologist with expertise in reading oncology PET/CT scans. For subjects assigned to sequence 1, questionnaire 2 should be completed before [⁶⁸Ga]Ga-PSMA-11 PET/CT is performed. Refer to Section 16.4 for details.

9 Study discontinuation and completion

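### Management change attributed to [18F]CTT1057 is pooled over two scan sequences in which the physician's knowledge of the gallium scan differs by design; show it by sequence

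*SAP*

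**What the plan says.** SAP 2.6.1 defines the endpoint as the percentage of participants whose intended plan changes, attributed to "the PET/CT scan as assessed by pre-imaging questionnaire 1 and post-imaging questionnaire 2". A change is a difference in plan category between the two questionnaires. The analysis is: "The number and percentage of participants from the F-SAF with treatment plan change as defined above will be calculated". The same section also plans category counts for each questionnaire, shift tables, and change by local [18F]CTT1057 read. SAP 2.6 and Section 4 add the prior RP and prior curative-intent RT subgroups. None of these separates the two scan sequences.

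On timing, protocol Section 3 places the questionnaires "before (questionnaire 1) and within 14 days after (questionnaire 2) knowing the results of the" [18F]CTT1057 scan, for everyone. Protocol 8.5.1 adds a rule for one sequence: "For subjects assigned to sequence 1, questionnaire 2 should be completed before" the [68Ga]Ga-PSMA-11 scan. On order, "The 2 PET imaging procedures will be done at least 14 days apart", with gallium first in sequence 2.

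On what the physician may know, local review of standard-of-care images, gallium included, "will be performed to be used by the treating physician/Clinical Study Investigator for patient management decisions and overall assessment" (protocol Section 3). Protocol 6.4 blinds the local [18F]CTT1057 reader and the pathologist to gallium, but states no such blinding for the treating physician. It also says: "Treatment and PET/CT scan sequence assignment will be open to participants, investigator staff, persons performing the assessments, and the study team".

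**The concern.** The endpoint carries the name of one agent. Attribution rests on comparing two questionnaires, and Appendix 4 as shown lists management options with no item asking which scan prompted a change. What the percentage means therefore depends on what the physician knew at each questionnaire, and that differs between the randomised sequences.

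The documents treat gallium knowledge as relevant here: they blind the local [18F]CTT1057 reader to it and give sequence 1 its own timing rule. The analysis does not carry the distinction through. From the outputs in SAP 2.6.1 a reader cannot tell how much of the reported change comes from participants whose physician may already have had a PSMA PET result from the other tracer.

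**Working it through.** **What each sequence measures.**

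- *Sequence 1.* [18F]CTT1057 is on Day 1 and gallium at least 14 days later. With questionnaire 2 completed before the gallium scan (protocol 8.5.1), the change is from no gallium information to [18F]CTT1057 without gallium information.
- *Sequence 2, questionnaire 1 before the gallium result.* Both results can arrive between the questionnaires, so the change reflects both tracers jointly.
- *Sequence 2, questionnaire 1 after the gallium result.* The change is what [18F]CTT1057 adds to a known gallium PET.

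The documents fix questionnaire 1 only against the [18F]CTT1057 result, so either sequence 2 case is possible. Neither is the sequence 1 quantity.

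**Inputs.** Allocation is 1:1 (protocol Section 3). Planned size is 190 enrolled to give 152 evaluable (SAP Section 3). The documents give no expected change rate and no sample size for this endpoint. The 190 comes from the PPV calculation: an exact one-sided 2.5% binomial test of 0.20 against 0.33 first reaches 90% power at 122 PET-positive participants, and 122/0.8 = 152.5, 152.5/0.8 = 190.6. It reproduces and is not in dispute.

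**How many are affected.** Half of 152 to 190 is 76 to 95 participants in sequence 2. The F-SAF is everyone dosed with [18F]CTT1057, so 152, the evaluable target, serves only as a low case. Anyone lost after gallium in sequence 2 never enters the F-SAF, so that share could fall slightly below one half.

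**Effect on the pooled figure.** Let p1 and p2 be the change rates by sequence and w the sequence 2 share of the F-SAF.

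- Pooled = (1 − w)p1 + w·p2, so pooled − p1 = w(p2 − p1).
- With w = 1/2 this is (p2 − p1)/2, and zero if p1 = p2.
- Assumed examples: p1 = 40% and p2 = 20% gives 30%, 10 points below sequence 1. p1 = 20% and p2 = 40% also gives 30%, 10 points above it. p1 = p2 = 30% gives 30%, with no gap. The pooled figure cannot tell these apart.

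**Precision after splitting.** The largest standard error is at p = 0.5, sqrt(0.25/n):

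- n = 190: 3.6 points; n = 95: 5.1 points.
- n = 152: 4.1 points; n = 76: 5.7 points.
- The ratio in each pair is sqrt(2) = 1.41.

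The largest 95% half-width for p2 − p1 is 1.96·sqrt(0.5/n): 14.2 points with 95 per sequence and 15.9 with 76.

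Exact 95% half-widths for a single rate, at assumed rates of 20%, 30% and 50%, are 5.9, 6.7 and 7.3 points pooled (n = 190), and 8.5, 9.6 and 10.4 points in one sequence (n = 95).

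**The case against.** The strongest reply is that the asymmetry is unavoidable and that pure attribution was never promised. In sequence 2 gallium is always first, so a rule to complete questionnaire 2 before it could not apply; protocol 8.5.1 protects the only sequence that can be protected. The protocol also warns: "Any change in patient management plan between the questionnaire 1 and questionnaire 2 should not be based only on" the [18F]CTT1057 result. Other standard-of-care imaging can inform the physician in both sequences. The endpoint is secondary and descriptive, has no estimand, and is not tested.

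All of that stands. It limits the point to interpretation, but it does not remove the difference in gallium information between sequences. Randomisation balances the participants, not what the design lets the physician know.

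Stronger readings are tempting, but the documents do not support them:

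- *The lack of a sequence 2 timing rule is an oversight.* It follows from the scan order.
- *The word pre-imaging leaves the scan unidentified.* The definition and the timing text both anchor to [18F]CTT1057; only the position of questionnaire 1 relative to gallium is open.
- *The general 14-day window undermines sequence 1.* The specific rule in 8.5.1 narrows that window. A late questionnaire would be non-adherence, not a flaw in the plan.
- *No by-sequence output exists anywhere.* Some SAP text is not visible to us. The absence is established for 2.6.1 and the other visible sections.

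**Conclusion.** The point holds as one of interpretation. The planned percentage combines a sequence 1 quantity with a sequence 2 quantity that is either the joint effect of both tracers or the increment over gallium. About half the F-SAF is in sequence 2, and the pooled rate differs from the sequence 1 rate by about half the between-sequence difference.

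This assumes near-equal sequence shares in the F-SAF, and that physicians in sequence 2 can see the local gallium read as protocol Section 3 provides. A reader might infer that the pooled figure overstates or understates the tracer's impact. The documents give no change rates, so neither is shown, and the gap could be zero. The co-primary endpoints are unaffected. The change is still worth making, because it is cheap and lets the endpoint answer its own question.

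**What to change.** In SAP 2.6.1, present the change percentage, the shift table and the table by local read by randomised sequence, beside the overall figure. State that:

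- all of sequence 1, as randomised, is the cleaner estimate of change without gallium information, though other standard-of-care procedures may still contribute;
- the overall figure includes participants whose physician may have had the gallium result.

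Where questionnaire dates are held, describe the timing of questionnaire 1 against the gallium scan in sequence 2. Restricting sequence 1 to participants whose questionnaire 2 preceded gallium should be a sensitivity display only, because it selects on something that happens after randomisation.

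Cost: the by-sequence tables need no new data. Sequence is already a display factor for disposition (SAP 2.3.1) and all deaths (SAP 2.7.2). SAP 2.4.1 already uses the scan dates, but the documents do not show that questionnaire completion dates are captured, so the timing description is conditional on that. Each sequence-specific standard error is about 1.4 times the pooled one, and the between-sequence difference could carry a 95% half-width of 14 to 16 points. The split is for description, not for a test.
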